7.2.3.2 Sleep diary

The sleep diary is provided to the subject at V1 as an electronic hand-held device, programmed in the subject’s language, and must be completed at home every day for at least 7 consecutive days between V1 and V2. The self-administered sleep diary includes a morning and an evening questionnaire and VAS.

On each morning after the two PSG nights at V2, V3, V4, V5, V6 and V7, the subject will complete the sleep diary morning questionnaire and VAS.

On the second evening before the second PSG night at V2, V3, V4, V5, V6 and V7, the subject will complete the sleep diary evening questionnaire and VAS.

7.2.3.2.1 Morning and evening questionnaires

These questions collect information on self-reported sleep characteristics (sleep induction and maintenance) and bedtime and timing of study treatment intake.

For further details, see [Appendix 9](#).

7.2.3.2.2 Visual analog scale

The VAS collect information on quality of sleep, depth of sleep, morning sleepiness, daytime alertness, and daytime ability to function, by asking the subjects to report their feelings by placing a mark on a VAS.

Self-reported quality of sleep, depth of sleep and morning sleepiness are assessed in the morning. Self-reported daytime alertness and daytime ability to function are assessed in the evening.

For further details, see [Appendix 9](#).

7.2.4 Safety assessments

The definitions, reporting and follow-up of AEs and SAEs are described in [Section 9](#).

7.2.4.1 Weight and height

Height will be measured at V1 only and recorded in the eCRF.

Body weight will be measured at V1 and in the second morning of V7 (recommended within 24 hours after last dose of double-blind study drug intake) and recorded in the eCRF. BMI will be calculated according to the BMI formula (weight in kg/m²) and displayed automatically upon entry of weight and height in the eCRF.

7.2.4.2 Vital signs

Systolic and diastolic BP, pulse rate and body temperature will be measured non-invasively at each study visit (i.e., V1 as well as first evening and each morning at V2, V3, V4, V5, V6 and V7). Vital signs will be measured with the subject either in a supine or sitting position. It is recommended to allow the subject to rest for at least 5 minutes and to use the same position (supine or sitting) throughout the trial for an individual subject. The right or left arm may be used, but it is recommended to use the same arm throughout the trial.

Vital sign measurement and conditions will be collected in the eCRF.

7.2.4.3 Physical examination

Physical examination is to be performed at V1 and on the second morning of V7 (recommended within 24 hours after last dose of double-blind study drug intake) as well as on the first evening at V2, V3, V4, V5, V6 and V7. It includes the examination of the following body systems:

- Head, ear, nose and throat
- Eyes
- Neck
- Cardiovascular system
- Respiratory system
- Abdomen
- Skin
- Extremities
- Neurological system
- Musculoskeletal system

Other exams will be performed if indicated, based on medical history and/or symptoms.

Information for all physical examinations must be included in the source documentation at the study site. The observations must be recorded according to body system. In the event of an abnormality, the related signs (e.g., systolic murmur) and not the diagnosis (e.g., mitral valve insufficiency) must be recorded in the eCRF. Clinically relevant findings (other than those related to insomnia disorder), including smoking habits that are present prior to signing of informed consent, must be recorded on the Medical History eCRF form. Physical examination findings made after signing of informed consent that meet the definition of an AE [Section 9.1.1] must be recorded on the AE form of the eCRF.

7.2.4.4 Digit Symbol Substitution Test[®]

The DSST[®] is to be performed each morning after a PSG night at V2, V3, V4, V5, V6 and V7. The DSST[®] is a measure of attention, perceptual speed, motor speed, visual scanning and memory.

On a sheet of paper, the subject is given 120 seconds to complete as many substitutions as possible, entering a symbol in numbered boxes according to a key shown on the top of the sheet (9 symbols).

The centers are provided with eight different test versions that use the same symbols in a different sequence. At each administration, a different test version is assigned among the eight versions, in order to minimize the impact of symbol/coding learning from one test to the subsequent one.

The number of correct substitutions is recorded as the total DSST[®] score.

Actelion has been granted a license agreement for the use of the DSST[®]. For further details, see [Appendix 5](#)

7.2.4.5 Sheehan Disability Scale[®]

The SDS[®] is to be performed each morning after a PSG night at V2, V3, V4, V5, V6 and V7. The SDS[®] consists of three questions on impairment of work, social life, and family life/home responsibilities [[Appendix 7](#), [Sheehan 1996](#)]. The SDS[®] is a self-administered questionnaire on the hand-held device. Actelion has been granted the license agreement for the use SDS[®].

7.2.4.6 Karolinska Sleepiness Scale

The KSS is to be performed each morning after a PSG night at V2, V3, V4, V5, V6 and V7. The KSS will be used to assess next-day alertness [see [Appendix 8](#)]. The subject will be asked to mark his/her sleepiness on a 9-point scale. The scale has a range from 1 being ‘very alert’ to 9 being ‘very sleepy, great effort to keep awake, fighting sleep’. The KSS is a self-administered questionnaire on the hand-held device.

7.2.4.7 Columbia Suicide Severity Rating Scale[®]

The C-SSRS[®] is to be performed at V1 and on each morning after a PSG night at V2, V3, V4, V5, V6 and V7. The C-SSRS[®] is an instrument that reports the severity of both suicidal ideation and behavior [[Posner 2007](#)]. Suicidal ideation is classified on a 5-item scale:

1. wish to be dead
2. nonspecific active suicidal thoughts

3. active suicidal ideation with any methods (not plan) without intent to act
4. active suicidal ideation with some intent to act, without specific plan
5. active suicidal ideation with specific plan and intent

The C-SSRS[®] also captures information about the intensity of ideation, specifically the frequency, duration, controllability, deterrents, and reasons for the most severe types of ideation. In addition, the C-SSRS[®] captures information using yes/no question and answers on suicidal behavior, specifically actual, interrupted, and aborted attempts; preparatory acts or behavior; and if suicidal behavior was present during the assessment period. More than one classification can be selected provided they represent separate episodes. For actual attempts only, the actual or potential lethality is classified for the initial, most lethal, and most recent attempts. The C-SSRS[®] will be completed at all study visits. At V1 (screening) the C-SSRS[®] will be completed for the subject lifetime history of suicidal ideation and behavior. At all other visits, the C-SSRS[®] will be completed for ideation and behavior since the previous visit.

At each visit, the investigator will review the responses provided by the subject and assess the findings. The scale will be self-administered using the hand-held device in the presence of an adequately trained staff member.

Actelion has been granted the license agreement for the use of the electronic C-SSRS[®].

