3 OVERALL STUDY DESIGN AND PLAN

3.1 Study design

This is a multi-center, double-blind, randomized, placebo-controlled, five-period, five-treatment crossover, PSG dose-response Phase 2 study in elderly subjects with insomnia disorder.

In order to have approximately 50 subjects randomized, approximately 120 subjects will be screened (estimated screen failure rate is up to 60%). Subjects will be randomized 1:1:1:1:1 to five different sequences of five study treatments according to a Latin square design [see [Table 1](#)]. The five study treatments are oral fixed doses of AC-541468 5 mg (D1), 10 mg (D2), 25 mg (D3) and 50 mg (D4), and placebo (P).

Table 1 Latin square design sequences

		Periods				
		1	2	3	4	5
Sequence	1	Dose 4	Dose 2	Dose 3	Dose 1	Placebo
	2	Dose 2	Placebo	Dose 4	Dose 3	Dose 1
	3	Dose 3	Dose 1	Dose 2	Placebo	Dose 4
	4	Placebo	Dose 4	Dose 1	Dose 2	Dose 3
	5	Dose 1	Dose 3	Placebo	Dose 4	Dose 2

The study will be conducted in approximately 10 sites in two countries (US and Germany).

Subjects who prematurely discontinue the study will not be replaced. Estimated dropout rate for the study is around 10%.

No interim analysis is planned during the conduct of the study. Subjects who complete the study or prematurely discontinue the study will be treated with standard of care according to investigator's opinion.

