3.1.1 Study phases

3.1.1.1 Screening phase

The **screening phase** lasts a minimum of 14 days and a maximum of 28 days. It starts with the signature of the Informed Consent Form (ICF) and ends with subject randomization. It includes the screening period (from Day –28 to Day –7) and the run-in period (from Day –14 to Day –1).

The **screening period** starts with V1, which occurs between Day –28 and Day –14 and is followed by the completion of the screening sleep diary for at least 7 consecutive days at home and until V2.

The **run-in period** occurs between Day –14 and Day –1 and starts with V2. V2 consists of two consecutive PSG nights on single-blind placebo treatment occurring between Day –14 and Day –6. V2 is followed by 5 to 12 days at home with no treatment.

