3.1.1.2 Double-blind treatment phase

The double-blind **treatment phase** starts with the first dose of study treatment in the first evening of the Randomization visit (V3) and ends in the second morning of V7. It consists of five **treatment periods**, each consisting of two consecutive PSG nights on the assigned study treatment followed by a 5- to 12-day washout.

The **End of Treatment (EOT)** is reached in the second morning of V7, after the last dose of double-blind treatment and after all morning assessments have been performed.

The **safety Follow-up phase** starts after the EOT and lasts at least 30 days (i.e., until the second follow-up telephone call). A first telephone call is done 5 days (+ 7 days) after EOT to collect TEAEs from the last study treatment dose.

[figure not shown]
The **End of Study (EOS)** for a single subject is defined as the date of the 30-day follow-up telephone call. If a subject withdraws consent and does not wish to participate in the study any longer, EOS is the date of consent withdrawal for this subject. If a subject is declared lost to follow-up [see also Section 8.2], EOS is the date of last successful contact for this subject.

Unscheduled visits are allowed to take place anytime during the study, in which case study-related information will be collected.

The visit schedule and protocol-mandated procedures will be performed according to the table of assessments [Table 3] and are described in Section 7.

The overall study design is depicted in [Figure 1].

Figure 1 Study design

V = visit; — polysomnographic (PSG) nights; D = dose; P = placebo.

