10.3.5 Analysis of the safety variables

All safety analyses will be performed on the SS, by dose, using descriptive statistics. All safety data will be listed, with flags for quantitative abnormalities.

Observations and assessments (e.g., AEs, laboratory data) occurring within a treatment period (from the time of dosing to the time immediately prior to the next dose) will be assigned to the dose taken in that period.

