### **10.5.5 Columbia Suicide Severity Rating Scale**

The Columbia Suicide Severity Rating Scale® (C-SSRS) is an instrument that evaluates suicidal ideation and behaviors.

The C-SSRS outcome categories are provided below. Each category has a binary response (yes/no) and are numbered and ordered below for convenience.

- 1 – Wish to be Dead
- 2 – Non-specific Active Suicidal Thoughts
- 3 – Active Suicidal Ideation with Any Methods (Not Plan) without Intent to Act
- 4 – Active Suicidal Ideation with Some Intent to Act, without Specific Plan
- 5 – Active Suicidal Ideation with Specific Plan and Intent
- 6 – Preparatory Acts or Behavior
- 7 – Aborted Attempt

- 8 – Interrupted Attempt
- 9 – Actual Attempt (non-fatal)
- 10 – Completed Suicide

Self-injurious behavior without suicidal intent is also a C-SSRS outcome (although not suicide-related) and has a binary response (yes/no).

Categories 1–5 relate to suicidal ideation and a score of 0 is assigned if no suicidal ideation is present. Categories 6–10 relate to suicidal behavior.

Number (%) of subjects with suicidal ideation, suicidal behavior, and/or self-injurious behavior without suicidal intent based on the C-SSRS during double-blind treatment will be tabulated. Percentages will be based on the number of subjects with at least one post-baseline C-SSRS assessment.

Shifts from baseline showing any changes in suicidal ideation and suicidal behavior in each treatment period will also be provided. Subjects will be summarized under the worst of the following three categories, shown here in the order from best to worst: 1) No suicidal ideation or behavior, 2) Suicidal ideation only, and 3) Suicidal ideation and behavior. Suicidal ideation includes any one of the five suicidal ideation events (categories 1–5). Suicidal behavior includes any one of the five suicidal behavior events (categories 6–10).

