### **13.2 Treatment period**

A treatment period is defined as the time from the start of the treatment period [see Section 13.1] until the start of the next treatment period. The end of the last treatment period (e.g., the fifth treatment period or an earlier treatment period if subject prematurely discontinued) is the date of first safety follow-up telephone call, or 12 days after the last study treatment intake, whichever is earlier.

After the single-blind placebo treatment period, subjects are to receive one of 5 study treatments in each of the 5 double-blind treatment periods in order of the sequence they are randomized to.

These treatment periods are used to assign assessments/events to dose groups (including single-blind placebo).

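### The first scheduled C-SSRS of each period looks back mostly over the previous treatment's washout but is assigned to the new dose, which misplaces washout findings in the by-dose C-SSRS tables

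*Protocol*

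**What the plan says.** **Recall and timing.** Protocol 7.2.4.7 says the C-SSRS "is to be performed at V1 and on each morning after a PSG night at V2, V3, V4, V5, V6 and V7". At V1 it covers lifetime history. At all later visits it "will be completed for ideation and behavior since the previous visit". Table 3 of the Protocol shows no C-SSRS on the first evening of V3 to V7 and none at the follow-up calls.

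**Spacing.** The treatment periods are described in Protocol 3.1.1.2 as "each consisting of two consecutive PSG nights on the assigned study treatment followed by a 5- to 12-day washout". Before V3, Protocol 3.1.1.1 says "V2 is followed by 5 to 12 days at home with no treatment".

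**Assignment to dose.** Under Protocol 10.3.5, an observation or assessment occurring within a treatment period "will be assigned to the dose taken in that period", and a period runs from dosing until just before the next dose. SAP 13.2 defines a period as start of period to start of next period and adds: "These treatment periods are used to assign assessments/events to dose groups (including single-blind placebo").

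**Reporting.** C-SSRS incidence is a named safety endpoint per treatment period (Protocol 6.2) and is summarized by dose (Protocol 10.3.5.6). SAP 10.5.5 tabulates ideation and behavior during double-blind treatment, and also says: "Shifts from baseline showing any changes in suicidal ideation and suicidal behavior in each treatment period will also be provided". It has no rule for a recall window that crosses a period boundary, and SAP 12.3 lists no clarification.

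**The concern.** The assignment rules go by when an assessment is done. That works for a blood pressure or an ECG, which describes the moment of measurement. A C-SSRS rating describes an interval, and here most of that interval lies in the previous period. Both documents count the washout as part of the earlier period, so the C-SSRS tables depart from the plan's own principle of attribution.

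A Latin square might be expected to spread the error evenly over the doses. It does not here, because the treatment that precedes each dose is far from balanced in Table 1. The comparison most affected is the one a safety reader looks at first, 50 mg against placebo. Suicidal thoughts and behaviors are an adverse event of special interest in this trial, so the placement of even a few positive responses matters.

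**Working it through.** **Check of the inputs.** Protocol 3.1.2 gives the double-blind phase as 30 to 58 days. Five periods of 2 days plus four washouts of 5 to 12 days give 10 + 4 × 5 = 30 and 10 + 4 × 12 = 58. The spacing is therefore read correctly. The documents give no figure for the C-SSRS itself.

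**Share of the recall window that is washout.** Let w be the washout in days, 5 to 12.

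- First-morning rating: w / (w + 1). This is 5/6 = 83% and 12/13 = 92%.
- Both mornings of a period together: w / (w + 2). This is 5/7 = 71% and 12/14 = 86%.

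In hours, intake is 30 minutes before lights off, followed by 8 hours in bed and a rating 30 to 60 minutes after lights on: 9 to 9.5 h. At 9.5 h, time on the new dose is 9.5 / (5 × 24 + 9.5) = 7.3% of the first-morning window with a 5-day washout, and 9.5 / (12 × 24 + 9.5) = 3.2% with a 12-day washout. These two figures describe the first-morning rating only.

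**What comes before and after each treatment** (Table 1, sequences 1 to 5 in order, equal allocation):

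| Treatment | Preceded by | Followed by |
|---|---|---|
| Placebo | 5, 10, 10 mg, run-in, 25 mg | none, 50, 50, 50, 50 mg |
| 5 mg | 25, 25, 25, 50 mg, run-in | placebo, none, 10, 10, 25 mg |
| 10 mg | 50 mg, run-in, 5, 5, 50 mg | 25 mg, placebo, placebo, 25 mg, none |
| 25 mg | 10, 50 mg, run-in, 10, 5 mg | 5, 5, 5 mg, none, placebo |
| 50 mg | run-in, placebo, placebo, placebo, placebo | 10, 25 mg, none, 5, 10 mg |

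**Reading the table.**

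- The 50 mg row takes in placebo washout in four sequences and the run-in interval in one. It never takes in an active-dose washout.
- The placebo row takes in active-dose washout in four of five sequences. As a share of the time that row covers, this is 0.8 × 5/7 = 57% to 0.8 × 12/14 = 69%.
- The washout after 50 mg goes to 10 mg (two sequences), 25 mg (one) and 5 mg (one). In sequence 3, 50 mg is the last period and no C-SSRS is scheduled after it. Every treatment is last in one sequence, so each has one washout without a scheduled rating.

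**Contrast with adverse events.** SAP 10.1 assigns an adverse event by its start date. An episode in the washout after 50 mg in sequence 1 would then be a 50 mg event in the adverse event tables, while the C-SSRS rating that reports it would be counted under 10 mg.

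**The case against.** Four objections carry weight.

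1. **Other routes capture the events.** The investigator reviews the C-SSRS responses at each visit (Protocol 7.2.4.7). Events of special interest are collected until end of study and adjudicated blind by the safety board. They are summarized and listed separately, with assignment by start date (SAP 10.1). A dated washout event after 50 mg stays with 50 mg there. This stands as mitigation. It does not repair the C-SSRS tables, and the two displays can disagree.

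2. **Unscheduled visits.** These may take place at any time, and a C-SSRS done at one during the 50 mg washout would be assigned to 50 mg. A reader might infer that ideation after 50 mg can never appear in the 50 mg row. The documents do not support that; the point is limited to scheduled ratings.

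3. **Time is not drug effect.** With the elderly half-life of 9.9 h (Protocol 3.2), a 5-day washout is 120 / 9.9, about 12 half-lives. In a 12-day washout, 7 days lie outside the 5-day treatment-emergent window. This stands: no drug effect in the washout has been shown. Against it, the plan itself treats events up to 5 days after intake as treatment-emergent, which fills the whole of the shortest washout.

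4. **The nights on dose are included.** A reader might take 3% to 7% as the share of the whole 50 mg row that concerns 50 mg. With both mornings counted in days, the share on dose is 14% to 29%.

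It would also go too far to say that the safety objective is answered for the wrong dose. The C-SSRS tables are one descriptive display beside an event analysis that is assigned by start date.

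**Conclusion.** The point holds for the scheduled C-SSRS tables. As the rules stand, washout recall is systematically placed under the next treatment. The 50 mg row is mainly placebo or run-in washout plus the nights on dose, and the placebo row is mostly active-dose washout. The washout after 50 mg is spread over lower doses or has no scheduled rating.

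This rests on two readings. First, the general assignment rules apply to the C-SSRS, since SAP 10.5.5 makes no exception. Second, the first rating at each visit looks back to the previous numbered visit. The Protocol does not say whether the second-morning rating looks back to the first morning or to the previous visit; under the latter the washout is counted at both ratings. Few positive responses are to be expected, and the documents give no expected count. The matter should be corrected, but it does not undermine the trial's safety assessment as a whole.

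**What to change.** **Preferred.** Keep both morning ratings, which Protocol 1.4.2 lists among the risk-minimization measures. Add a self-administered C-SSRS with a since-last-visit look-back on the first evening of V3 to V7, before study drug intake. In SAP 10.5.5, assign that rating to the preceding period (run-in for V3). Let each morning rating look back only to the preceding C-SSRS, and assign it to the current dose.

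**If the schedule cannot change.** In SAP 10.5.5, assign positive findings by the onset established at the investigator's review, in line with the start-date rule in SAP 10.1. Show positives of unknown onset separately, as spanning washout and current dose. State the look-back of the second-morning rating.

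Under either option, footnote that the washout after period 5 has no scheduled C-SSRS.

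Moving the first-morning rating to the evening is not advised, because it would remove the reading between the two doses of a period. Assigning every first-morning rating to the preceding dose by default would misplace ideation that began on the first night of the new dose.

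**Cost.** One short questionnaire per visit on a device already in use, or onset dating of the few positive responses, plus a few sentences in SAP 10.5.5.

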4.4 Exclusion criteria

Subjects must not fulfill any of the following exclusion criteria. It is not permitted to waive any of the criteria for any subject (V1 and V2 in brackets refer to the visits when the criteria must be assessed):

1. Any current sleep disorder(s) other than insomnia, or any lifetime history of related breathing disorder, periodic limb movement disorder, restless legs syndrome, circadian rhythm disorder, REM behavior disorder, or narcolepsy (V1).
2. Self-reported usual daytime napping ≥ 1 hour per day, and on ≥ 3 days per week (V1).
3. Caffeine consumption ≥ 600 mg per day (V1) [see [Appendix 3](#)].
4. Shift work within 2 weeks prior to the screening visit, or planned shift work during study (V1).
5. Travel \geq three time zones within 1 week prior to the screening visit, or planned travel \geq three time zones during study (V1).
6. Hematology or biochemistry test results deviating from the normal range to a clinically relevant extent as per judgment of the investigator (V1, V2)
7. AST and/or ALT $> 2 \times$ the ULN and/or direct bilirubin $> 1.5 \times$ ULN (V1, V2).
8. Severe renal impairment: known or defined as estimated creatinine clearance < 30 mL/min, according to the 4-variable Modification of Diet in Renal Disease formula (V1, V2)
9. Unstable medical condition, significant medical disorder or acute illness within 1 month prior to the screening visit that in the opinion of the investigator could affect the subject's safety or interfere with the study assessments (V1).
10. Systolic blood pressure (BP) > 150 mmHg and diastolic BP > 90 mmHg (V1, V2).
11. Resting pulse rate < 50 or ≥ 100 beats per minute (V1, V2).
12. Any of the following conditions related to corrected QT (QTc) intervals (V1, V2):
 - 11.1 A prolonged QTc interval (QTc greater than 450 ms). In case of QTc greater than 450 msec on the first ECG, a second ECG recording will be performed after at least 30 minutes on the same day. If QTc is greater than 450 ms on the second ECG, the subject is not eligible.
 - 11.2 A history of additional risk factors for torsade de pointes (e.g., heart failure, hypokalemia, family history of long QT syndrome).
13. Any of the following conditions related to suicidality:
 - 12.1 Any suicidal ideation with intent with or without a plan at screening, i.e., answering "Yes" to questions 4 or 5 on the suicidal ideation section of the screening / Baseline version of the C-SSRS[®] (V1, V2).
 - 12.2 Lifetime history of suicide attempt (V1).

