### **13.4 Baseline**

Baseline is the last non-missing assessment performed or value measured before or on the day of first dose of double-blind study treatment, unless otherwise defined in the specific analysis section.

Subjects with no data on a particular parameter before the first treatment administration will have a missing baseline (and change from baseline) for this parameter.

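### The C-SSRS shift table defaults to one V2 form as baseline but takes the worst of two forms in each period; this can tilt its absolute shift counts, depending on an unstated recall window.

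*Protocol*

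**What the plan says.** **Collection.** Protocol 7.2.4.7 says the C-SSRS "is to be performed at V1 and on each morning after a PSG night at V2, V3, V4, V5, V6 and V7". That gives three forms before double-blind dosing (V1 and two at V2) and two in each of the five treatment periods. The V1 form "will be completed for the subject lifetime history of suicidal ideation and behavior". At every later visit the scale "will be completed for ideation and behavior since the previous visit". Nothing is said about the window of the second form within a visit.

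**Analysis.** SAP 10.5.5 states: "Shifts from baseline showing any changes in suicidal ideation and suicidal behavior in each treatment period will also be provided". It adds: "Subjects will be summarized under the worst of the following three categories", these being neither ideation nor behavior, ideation only, and both. It does not say which form is baseline.

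**Default.** SAP 13.4 fills the gap unless a section says otherwise: "Baseline is the last non-missing assessment performed or value measured before or on the day of first dose of double-blind study treatment". SAP 13.2 assigns assessments to a dose by treatment period, from the first dose of a period to the start of the next.

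**Comparators.** For DSST, KSS and SDS, collected on the same mornings, SAP 10.5.1 to 10.5.3 override the default and use both V2 mornings. SAP 12.3 records no clarification for the C-SSRS.

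**Eligibility.** Exclusion 13 (protocol 4.4) removes subjects answering yes to ideation items 4 or 5, and those with a lifetime suicide attempt. Items 1 to 3 are not excluded by that criterion. It bases the V1 and V2 checks "on the suicidal ideation section of the screening / Baseline version" of the C-SSRS.

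**The concern.** A shift table is meant to separate ideation already present before dosing from ideation first seen afterwards. It does that fairly only if the before and after sides have a similar chance of picking up the same stable state. Here the before side is one form and the after side is the worse of two. A subject whose reporting of passive ideation comes and goes has more chances to be positive in a period than at baseline, so part of the none-to-ideation cell could come from counting alone.

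Suicidal thoughts and behaviors are adverse events of special interest in this trial. A reader of the report would look at this table to judge whether ideation is new.

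**Working it through.** The plan gives no figure for this table, so there is nothing to reproduce. The check applies its rules and then illustrates their size. All probabilities below are assumptions; the documents give no ideation rate.

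**1. Which form is baseline.** No C-SSRS is scheduled on the V3 evening, and the first V3 form is completed the morning after the first double-blind dose. The last form before dosing is therefore the second V2 morning, or an earlier form if that one is missing.

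**2. Rules applied to example subjects.** Each subject has ideation on one pre-dose form and again on one form in every period. The entries are none-to-ideation shifts out of 5 periods.

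| Pre-dose ideation recorded on | Last V2 form (as planned) | Worst of both V2 forms | Worst of V1 and V2 |
|---|---|---|---|
| V1 only | 5 | 5 | 0 |
| First V2 morning only | 5 | 0 | 0 |
| Second V2 morning | 0 | 0 | 0 |

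The second row can occur only if the second V2 form does not reach back over the first V2 morning. In every row the ideation must be reported afresh in the period; nothing is carried forward.

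**3. Size if each form looks back only to the form before it.** Let p be the chance that a form is positive, equal and independent across forms, with no drug effect.

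- Upward shift, planned baseline: (1−p) × [1−(1−p)²]
- Downward shift, planned baseline: p × (1−p)²
- Ratio of the two: (2−p)/(1−p)
- Either direction, worst of both V2 forms: (1−p)² × [1−(1−p)²]

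| p | Up, planned | Down, planned | Ratio | Each direction, worst of V2 |
|---|---|---|---|---|
| 0.05 | 9.3% | 4.5% | 2.05 | 8.8% |
| 0.10 | 17.1% | 8.1% | 2.11 | 15.4% |
| 0.20 | 28.8% | 12.8% | 2.25 | 23.0% |
| 0.50 | 37.5% | 12.5% | 3.00 | 18.8% |

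At low p, most of the tilt is downward shifts that the single baseline form misses. With 50 subjects and p = 0.05, the planned rule expects 50 × 0.0926 = 4.6 up and 50 × 0.0451 = 2.3 down per treatment. The two-form baseline expects 50 × 0.0880 = 4.4 each way.

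**4. Size if the second V2 form looks back to V1.** Table 3 of the protocol puts 7 to 21 days at home between V1 and V2, and 5 to 12 days between later visits. Adding two nights, baseline spans about 9 to 23 days and a period about 7 to 14. Assume independent days with a 0.5% daily chance, so that P(positive over d days) = 1 − 0.995^d: 4.4% for 9 days, 3.4% for 7, 6.8% for 14 and 10.9% for 23.

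- Baseline 9 days, period 7: up 0.956 × 0.034 = 3.3%; down 0.044 × 0.966 = 4.3%.
- Baseline 9 days, period 14: up 0.956 × 0.068 = 6.5%; down 0.044 × 0.932 = 4.1%.
- Baseline 23 days, period 14: up 0.891 × 0.068 = 6.0%; down 0.109 × 0.932 = 10.2%.

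A modest upward tilt remains only when a short baseline window meets a long period; otherwise the direction reverses.

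**The case against.** **The literal wording favors the plan.** The look-back is to the previous visit, and protocol 3.1.1.1 treats V2 as one visit made up of two nights. Read so, the second V2 form reaches back to V1, already covers the first V2 morning, and has a window comparable to or longer than a period's. This stands, and is why the tilt is conditional. What remains is that the protocol never states the window for a second form within a visit.

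**The single-form baseline is an inference.** It comes from the SAP default because 10.5.5 is silent, and the worst-category rule is not expressly confined to treatment periods. True, but 13.4 is written for exactly this case, and the worst category over one form is that form. The protocol 10.2 default, a mean of the last two values, does not suit a category.

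**A reader might infer a large excess on every dose.** Setting a one-day baseline against a 7-to-14-day period, with an assumed daily chance of 0.5% to 2%, gives upward shifts of 0.995 × 0.0345 = 3.4% to 0.98 × 0.2464 = 24.1%. Most of that is not caused by the baseline rule. Perfectly matched windows give 0.9655 × 0.0345 = 3.3% and 0.7536 × 0.2464 = 18.6%, so the attributable part is about 0.1 to 5.6 points. The daily rates have no source in the documents, and one day is the non-literal reading.

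**A reader might infer a false drug signal.** All five treatments share the same baseline for each subject, and the Latin square gives every treatment in every period. The rule raises counts on placebo as on drug and does not bias the contrast. The protocol's C-SSRS endpoint is incidence, which SAP 10.5.5 tabulates without a baseline, and events of special interest come from the adverse event page and Independent Safety Board adjudication.

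**Persistent ideation is not caught by this.** A subject who reports ideation on every form is positive at baseline and does not shift. Only intermittent reporting is affected. This also stands.

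**Conclusion.** The point holds as a small, conditional asymmetry in one descriptive safety table. By default the SAP compares one baseline form with the worst of two forms per period, although it uses both V2 mornings for three other scales.

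If the second form of a visit looks back only to the previous form, apparent worsening is about 2 to 3 times apparent improvement on every treatment, for an assumed chance per form of 5% to 50%, equal and independent across forms, with no drug effect. Persistence of ideation would shrink the number of shifts; longer look-back on the first form of each period would widen the ratio. If the second V2 form looks back to V1, the tilt largely disappears and can reverse.

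The documents do not support reading this as a drug signal or as bias between dose and placebo. Nor are V1 data lost: SAP section 10 lists all safety data. V1-only ideation produces the same shifts whether baseline is one V2 form or the worst of both.

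The exclusion 13 wording is a separate inconsistency. It names a screening / baseline version at V2, where protocol 7.2.4.7 provides a since-previous-visit form. It has no bearing on the size of the tilt.

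**What to change.** 1. In SAP 10.5.5, define the shift-table baseline as the worst category over the two V2 morning forms. Under the equal-chance illustration this makes upward and downward shifts equal.
2. State the recall window of the second form within a visit, at V2 and at V3 to V7.
3. Show V1 lifetime history separately as context, with a note that this displays V1-only ideation but does not remove its shifts. Merging V1 into the baseline would set a lifetime window against one of days.
4. Separately, reconcile the form version named in exclusion 13 with protocol 7.2.4.7, so that both describe the same V2 assessment.

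The cost is a sentence or two in the SAP, one extra descriptive row and one protocol wording correction. No new data are needed.
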